8 ANALYSIS OF SAFETY

8.1 Extent of Exposure

The number of days of exposure to study medication will be listed and summarized using descriptive statistics and using counts and percentages of the number of patients in each exposure category listed in section 3.5.1.

8.2 Adverse Events

Treatment-emergent AEs (TEAEs) occurring in patients from the Safety Population will be presented in data listings with an indication of whether the AE start date occurred during Period 1, Period 2, or the Follow-up Period. Any AEs that were recorded in the CRF from patients who were not included in the Safety Population will be listed separately and will not be included in any subsequent listings or tables.

A summary overview of TEAEs will be provided, which will present the number and percentage of patients satisfying each of the following categories. This table will be presented for Period 1 and Period 2 (see 3.2.1 for derivation) separately and for Period 1 and Period 2 combined and for the Follow-up Period, using the Safety Population.

- Any TEAEs
- Maximum severity of TEAEs
- Study drug-related TEAEs
- All TE SAEs
- All TE study drug-related TE SAEs
- TEAEs leading to death
- TEAEs leading to withdrawal of study medication

The number and percentage of patients with TEAEs will be summarized by their MedDRA preferred term within system organ class. This will be presented for Period 1 and Period 2 separately and for Period 1 and Period 2 combined and for the Follow-up Period, using the Safety Population. In this summary, any patients reporting multiple episodes of the same TEAE (i.e. same preferred term) within a single period, will be counted once. It is acknowledged that any conclusions that arise from a comparison of AEs reported during Period 1 and Period 2 may be limited due to the consecutive nature of the periods. A similar summary will be provided for study drug-related TEAEs.

The number and percentage of patients with TEAEs will be summarized by reported severity (*Severity = 'Mild', 'Moderate', 'Severe'*) within each MedDRA preferred term within system organ class. This will be presented for Period 1 and Period 2 separately and for Period 1 and Period 2 combined and for the Follow-up Period, using the Safety Population. In this summary, any patients reporting multiple episodes of the same TEAE (i.e. same preferred term) within a single period, will be counted once against the most severely reported category.

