8.1.2 Secondary Endpoints

The secondary endpoints of the study are:

- The change from baseline of VO₂MAX at the end of study-drug dosing Period 1 compared to the change from baseline at the end of study-drug dosing Period 2.
- An evaluation of the change in VO₂MAX at the end of study-drug dosing Period 1 compared to baseline will be performed.
- The change from baseline of the QTcF interval at the end of study-drug dosing Period 1 compared to the change from baseline at the end of study-drug dosing Period 2

- The change from baseline at the end of study-drug dosing Period 2 in the Six-Minute Walk Test (6MWT) and change from baseline at the end of study-drug dosing Period 1 compared to the change from baseline at the end of study-drug dosing Period 2
- Safety data (AEs, ECG abnormalities, routine laboratory safety test of blood, vital signs, and concomitant medication and patient withdrawals) during study-drug dosing Period 1 compared to study-drug dosing Period 2

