3.2 Safety Variables

3.2.1 Adverse Events

Adverse events (AEs) were to be spontaneously reported or elicited during open-ended questioning, examination, or evaluation of a patient. The protocol (section 7.1) defines an AE as any untoward medical occurrence associated with the use of a drug in humans, whether or not considered drug related.

The following information was to be captured for all AEs:

- Start date

- End date (or ongoing status, if ongoing at the end of study)
- Outcome (Recovered/Resolved; Recovered/Resolved with Sequelae; Recovering/Resolving; Not Recovered/Not Resolved; Fatal; Unknown)
- Relationship to study treatment (Definitely Related; Probably Related; Possibly Related; Unrelated)
- Action taken with study treatment (Drug Withdrawn; Drug Interrupted; Dose Reduced; Dose Not Changed; Dose Increased; Other; Not Applicable)
- Any other action taken (No; Yes)
- Caused study discontinuation (No; Yes)
- Severity (Mild; Moderate; Severe)
- Seriousness (No; Yes)
- Adverse Device Effects (No; Yes)
- Is the event an overdose (No; Yes)
- Is the event a cancer event (No; Yes)

If the investigator deemed the AE to be serious, the reason(s) for being considered serious would be recorded in the eCRF.

AEs will be coded using the Medical Dictionary for Regulatory Activities (MedDRA).

A treatment-emergent adverse event (TEAE) is defined as any AE with a recorded start date on or after the date of the first dose of study medication. Treatment emergent (TE) status of AEs with a partial start date will be determined using available incomplete date information. For example, if the AE has a missing day field but the non-missing month and year fields place the start of the AE after the start of study medication, then the AE will be designated TE. For AEs where the available partial date information is inconclusive (for example, missing day but available month and year are equal to the month and year of start of study medication) then the AE will be classified as TE. In particular, AEs with a completely missing start date will be assumed to be TE (unless the AE stop date places the AE prior to starting treatment).

TEAEs will be split further according to whether the AE start date occurred during Period 1 or Period 2 of the Treatment Epoch, or during the Follow-up Epoch.

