4 ANALYSIS POPULATIONS

4.1.1 *Safety Population*

The Safety Population will include all patients who receive study drug.

4.1.2 *Modified Intention to Treat Population*

The Modified Intention to Treat Population (MITT) will include all patients who receive study drug and have at least one post-Baseline efficacy assessment.

4.1.3 *Completer Population*

The Completer Population will include all patients who receive study drug and complete all study procedures at Baseline, end of Period 1 and end of Period 2 and have their Period 2 CPEX assessment within 7 days of the target day of 113.

4.1.4 *Pharmacokinetic Population*

The Pharmacokinetic Population will include all patients who receive study drug and had at least one plasma sample collected.

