6 ANALYSIS OF DISPOSITION AND PATIENT CHARACTERISTICS

6.1 Disposition and Analysis Populations

The reason given for each screen failure (did not satisfy all inclusion/exclusion criteria, withdrawal by patient, physician decision, adverse event, lost to follow-up, other) will be listed and summarized.

A data listing will be presented to indicate which patients satisfied the criteria for inclusion in the Safety, Modified Intention to Treat, Completer and Pharmacokinetic Populations. The number of patients included in each population will be summarized using counts and percentages, with percentages based on Safety Population as denominator.

Patient disposition will be presented for all patients in the Safety Population. The number and percentage of patients in each of the following disposition categories will be presented, with percentages based on Safety Population as denominator:

- Patients who completed screening (number of patients only)
- Patients who started study treatment
- Patients who completed Period 1 treatment
- Patients who completed Period 2 treatment
- Patients who completed the study as planned to the follow up visit

For patients in the Safety Population who withdraw early from the study treatment or withdrew from the study before the follow up visit, the primary reason for the early withdrawal will be listed and summarized.

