8.3 Safety Laboratory Parameters

Laboratory chemistry and hematology data will be listed for each subject in the Safety Population with values outside the normal reference ranges flagged as low or high.

Descriptive statistics of each chemistry and hematology parameter will be presented for the Safety Population, showing the observed visit and change from Baseline to each visit value.

The number of patients with reported transaminases (AST, ALT, Alkaline phosphatase, total bilirubin) that are outside the defined ULN threshold multiples (see section 3.2.2) will be summarized showing the counts and percentages for Period 1 and Period 2 separately and for Period 1 and Period 2 combined, using the Safety Population.

Pharmacogenetic data (CYP2D6 genotyping at screening) will be listed for each subject in the Safety Population. Any incidences of polymorphisms (see section 3.4.5) will be summarized for the Safety Population.

A cross-tabulation will be displayed to show the agreement between the CYP2D6 genotyping status (PM, IM, EM, UM) and the phenotype status defined from the ratio of the CIS:PEX ratio (<0.4 , ≥ 0.4) from the Week 1 plasma levels (see section 3.3.1).

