8.5 Vital Signs

Vital signs data from patients in the Safety Population will be presented in a data listing. The listing will identify the Baseline value, and present the visit value and change from Baseline to

each visit value, for each parameter. Values outside the thresholds indicated in section 3.2.4 will be identified on the listing.

Descriptive statistics of each vital signs parameter will be presented for the Safety Population, showing the observed visit and change from Baseline to each visit value. The number of patients who report a vital signs parameter outside the thresholds at any visit during Period 1, or Period 2 will be summarized using counts and percentages for the Safety Population.

Shift tables will be used to indicate the number of patients with systolic or diastolic blood pressure or heart rate values that changed status relative to the thresholds identified above (section 3.2.4) between Baseline and any vital signs assessment during each period.

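### SAP 8.2 bases Period 2 adverse-event percentages on all treated patients, so anyone who leaves in Period 1 lowers the Period 2 rate; the effect is modest (at most 9.1% relative under the plan) but avoidable

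*SAP*

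**What the plan says.** **Adverse events.** SAP 8.2 plans an overview, a preferred-term table and a severity table. For the second it says: "The number and percentage of patients with TEAEs will be summarized by their MedDRA preferred term within system organ class". All three are to be shown for Period 1 and Period 2 separately, and "for Period 1 and Period 2 combined and for the Follow-up Period, using the Safety Population".

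**The population.** SAP section 4 states: "The Safety Population will include all patients who receive study drug". The other sets defined there are a modified intention-to-treat, a completer and a pharmacokinetic population. None is specific to a period.

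**Allocation to periods.** SAP 3.2.1 assigns events by onset: "TEAEs will be split further according to whether the AE start date occurred during Period 1 or Period 2" of the treatment epoch, or in follow-up.

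**Measured flags.** SAP 8.3 says the liver-test threshold flags "will be summarized showing the counts and percentages for Period 1 and Period 2 separately", and combined, again in the Safety Population. SAP 8.5 counts patients with a vital-sign value outside the thresholds "at any visit during Period 1, or Period 2 will be summarized using counts and percentages for the Safety Population". In SAP 8.6 the shift tables are by period; the threshold counts are not stated to be.

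**Why the comparison has standing.** Protocol 8.1.2 lists as a secondary endpoint the safety data (including adverse events, laboratory tests, vital signs and "patient withdrawals) during study-drug dosing Period 1 compared to study-drug dosing Period 2".

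**The concern.** Period 2 targets 300-500 ng/mL and Period 1 targets 100-300 ng/mL. Protocol 2.8 gives as a reason for the study that the lower range might be as effective and safer. A reader will therefore set the Period 2 adverse-event column beside the Period 1 column.

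Every treated patient is at risk in Period 1. Only those who go on to Period 2 are at risk of a Period 2 onset. Some loss in Period 1 is built in: Protocol 4.4.2 withdraws phenotypic poor metabolisers on the Day 8 result, other withdrawals are possible, and Protocol 8.5 allows no replacement. Dividing both columns by the same N treats the leavers as Period 2 patients without events. That makes the higher-exposure period look somewhat better relative to the lower one than it was.

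**Working it through.** **Inputs**

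- N = 33 treated and 30 expected to complete 16 weeks (Protocol synopsis). I assume that all 33 enrolled are dosed.
- k = number who leave in Period 1; M = N - k enter Period 2. The documents do not split the losses by period, so k is shown as a range.
- x = patients with at least one TEAE starting in Period 2. Leavers contribute none, because allocation is by onset within the treatment epoch.

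**Plan figure.** The documents state no safety percentage. The only planning figure that enters is the dropout allowance: (33 - 30)/33 = 3/33 = 9.1%.

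**Formula for adverse events**

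Reported rate = x/N = (x/M) × (M/N). Relative understatement = 1 - M/N = k/N.

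| k leaving in Period 1 | M | M/N | Relative understatement | Shift at an assumed 30% rate |
|---|---|---|---|---|
| 0 | 33 | 1.000 | 0% | 0 points |
| 1 | 32 | 0.970 | 3.0% | 0.9 points |
| 2 | 31 | 0.939 | 6.1% | 1.8 points |
| 3 | 30 | 0.909 | 9.1% | 2.7 points |

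The last column is 30 × k/33. The last row is the limit under the plan, because it puts all three expected losses in Period 1.

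**Examples at k = 3**

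- 3, 9 and 15 patients with an event read 9.1%, 27.3% and 45.5% on 33, but 10.0%, 30.0% and 50.0% on 30.
- With assumed true rates of 30% in Period 1 and 40% in Period 2, the reported Period 2 rate is 40 × 30/33 = 36.4%. A 10-point excess appears as 6.4 points.
- The order can change when the rates are close. Take 12/33 = 36.4% in Period 1 and 11 patients with events in Period 2. On all treated, Period 2 reads 11/33 = 33.3% and looks lower. On patients at risk it is 11/30 = 36.7%, marginally higher. With k = 1 no pair of counts reverses in this way.

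**Poor-metaboliser withdrawals alone.** At the 1% incidence in Protocol 2.7.2, the expected number is 33 × 0.01 = 0.33, and the chance of at least one is 1 - 0.99^33 = 28%. Most of any effect would have to come from other withdrawals.

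**Measured flags.** Let k1 and k2 be the treated patients with no value in Period 1 and Period 2. Dividing both periods by N multiplies the Period 2 to Period 1 ratio by (N - k2)/(N - k1). Post-baseline chemistry is scheduled in the dosing periods only at Weeks 8 and 16, and vital signs start at Week 2 (Protocol Table 6.2). A patient who leaves before the first measurement, with no withdrawal sample obtained under Protocol 6.11, counts in both k1 and k2. If k1 = k2 = 3, the factor is 30/30 = 1: both percentages are 9.1% too low in relative terms, but the comparison is undistorted. If withdrawal values are obtained, k2 exceeds k1 and Period 2 is understated relative to Period 1. If a patient misses the Week 8 sample but has one at Week 16, k1 rises and the bias goes the other way.

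**The case against.** **The denominator is inferred.** SAP 8.2, 8.3 and 8.5 name an analysis set and do not state a denominator. SAP 6.1, for disposition, does state one ("with percentages based on Safety Population as denominator"). SAP 5.4 puts table mock-ups in separate documents, where column sizes may be set. It is true that this is a reading. It is the natural one, though, since the SAP gives no other base for these percentages. If the mock-ups use another, the SAP should say so.

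**Much of it can be recovered.** Counts appear beside percentages, disposition shows how many completed each period, listings flag the period of each event, and no test of adverse-event rates is planned. This limits the harm. It still leaves the reader to rebuild the percentages. The SAP's own caution about comparing periods concerns only that they are consecutive; it does not mention patients no longer at risk.

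**The effect is small.** At k = 3 and a 30% rate the shift is 2.7 points, less than one patient in 33 (3.0 points). This stands, and it sets the weight of the point.

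**Stronger readings that the documents do not support.** A reader might infer the following:

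- *All by-period safety flags are biased in favour of Period 2.* The assessment schedule does not support this for laboratory flags, or for vital signs in the earliest leavers.
- *The Follow-up column understates the risk of higher exposure.* Follow-up is off drug. The TEAE definition has no end date and serious events are collected for 30 days after the last dose, so early leavers may contribute events there.
- *The ECG threshold counts in SAP 8.6 have the same fault.* They are not stated to be by period.
- *The distortion could be twice as large.* Six losses in Period 1 would give 6/33 = 18.2%, but that is double the dropout planned for the whole trial.

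**Conclusion.** The point holds for adverse events. Following SAP 8.2 as written understates Period 2 TEAE incidence by k/N relative to Period 1. Under the plan this lies between 0% and 9.1%, and it reaches 9.1% only if all three expected losses fall in Period 1. For a given k the relative size does not depend on the event rate. The direction is fixed whenever at least one patient leaves in Period 1 and at least one event occurs in Period 2.

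This rests on three assumptions: that the Safety Population is the percentage base, that all 33 enrolled are treated, and that dropout is close to plan. The 30% and 40% event rates above are illustrations and do not come from the documents.

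For liver-test and vital-sign flags the all-treated base is unsuitable, because it counts patients with no measurement as having no flag. The net direction between periods cannot be stated in advance. The matter is modest in size, but it affects a named secondary endpoint and is simple to put right.

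**What to change.** - **SAP 8.2, Period 2 column:** use as denominator the patients who took at least one dose in Period 2. For the Follow-up column, use those who entered follow-up. Show n at the head of each column.
- **SAP 8.3, 8.5 and the by-period shift tables in 8.6:** use patients with at least one post-baseline value of that parameter in that period.
- **Like-for-like column:** beside the Period 2 adverse-event rates, show Period 1 rates restricted to patients who entered Period 2.
- **Note with the tables:** state that this restriction only partly addresses selection, because those who reach Period 2 are those who stayed on drug. It also does not remove the confounding of period with time on drug.

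The cost is SAP wording, table headers and one extra column. Period-level tablet accounting, days of exposure and period completion are already planned, so no new data are needed.

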2.8 STUDY RATIONALE

This is an open-label, phase II study to confirm the optimal dosing regimen of PEX for use in a future phase III study in patients with HCM. The previous study [Abozguia, 2010] in HCM patients demonstrated that a safe and effective plasma concentration for PEX was 150-600 ng/mL. However, a more refined dosing study to evaluate safety and efficacy at low (100-300 ng/mL) and high (300-500 ng/mL) plasma PEX levels has not yet been performed. Potentially, equal efficacy with improved safety could be achieved at lower concentrations of PEX.

A population pharmacokinetic (PK) evaluation of the PK data from the PEX-TQT study was done to identify and characterize patient factors influencing PEX PK and the magnitude of unexplained PK variability [Mould, 2016]. Application of this newly developed model compared to a previously published model [Hussein *et al.*, 2001] showed the new model better describes PEX PK, particularly in extensive metabolizer (EM) and intermediate metabolizer (IM) groups.

The 2-compartment PK model developed from this exercise was used to predict drug exposures after single and multiple doses of PEX 70, 140, and 280 mg in all CYP2D6 genotypes [Mould, 2016]. Simulations of multiple dose administrations demonstrated that therapeutic levels of PEX in the range of 150-600 ng/mL for all the CYP2D6 genotypes eligible could be achieved in this study with doses of 70 to 280 mg daily. Figure 2.1 shows the initial response to 70 mg daily in IM, EM, and PM subjects, and clearly shows that all subjects, including phenotypic PM subjects can be safely dosed through two weeks without reaching

excessive PEX levels. However, conservatively, a blood sample to measure PEX and CIS levels will be obtained at day 8 to withdraw phenotypic PMs from the study. Then starting on day 15, PEX levels will continue to be measured every other week (Weeks 2, 4, 6, 8, 10, 12 and 14) in order to guide dose adjustment and to achieve the desired plasma concentrations. The following doses are expected to produce therapeutic concentrations in the majority of patients (PMs are being excluded from the study):

- Intermediate Metabolizers (IM): 70 to 140 mg daily
- Extensive Metabolizers (EM): 140 to 210 mg daily
- Ultra-rapid Metabolizers (UM): May require maximum doses of 210 (Period 1) or 280 (Period 2) mg daily. These subjects may not reach the target therapeutic level.

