8.4.2 Safety Analyses

8.4.2.1 Adverse Events

The original terms recorded on the subject's CRF by the Investigator for AEs will be standardized by assigning preferred terms from the Medical Dictionary for Regulatory Activities (MedDRA). The Investigator, however, should ensure that the original terms recorded accurately reflect their intended description. All AEs will be described by individual subject listings and summarized in frequency tables broken down by body system, preferred term and dose group.

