8.8 Pharmacokinetic Analysis

Pharmacokinetic data for PEX, CIS and TRANS, will be listed by patient and summarized for each sampling time point.

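### SAP 8.2 tabulates adverse events by study period only and leaves the protocol's dose-group breakdown undefined; no table shows events by attained dose or PEX level, or counts patients in the target range

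*SAP*

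**What the plan says.** Protocol 8.4.2.1 wants adverse events "summarized in frequency tables broken down by body system, preferred term and dose group". Dose group is not defined anywhere in the protocol. Among the secondary endpoints, Protocol 8.1.2 compares safety data "during study-drug dosing Period 1 compared to study-drug dosing Period 2".

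SAP 3.2.1 sets the column for each event: "TEAEs will be split further according to whether the AE start date occurred during Period 1 or Period 2 of the Treatment Epoch", or during follow-up. SAP 8.2 then gives its overview, preferred-term and severity tables the same layout: "This will be presented for Period 1 and Period 2 separately and for Period 1 and Period 2 combined and for the Follow-up Period". It warns that conclusions from the period comparison "may be limited due to the consecutive nature of the periods". It gives no warning about exposure outside the target range.

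On dose and level:
- SAP 8.1 summarizes total days on drug.
- SAP 3.5.1 derives an estimated daily dose for each of nine accounting intervals, and SAP 6.5 lists it without a summary.
- SAP 8.8 states: "Pharmacokinetic data for PEX, CIS and TRANS, will be listed by patient and summarized for each sampling time point".
- SAP 12 lists three changes from the protocol: the MITT population, early-withdrawal data, and ANCOVA in place of the t-test. The layout of the adverse event tables is not among them.

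**The concern.** Protocol 2.8 defines the study's question by plasma level: safety and efficacy at 100-300 versus 300-500 ng/mL, to settle a phase 3 regimen, with the possibility that lower levels give equal efficacy and better safety. Readers will use the Period 1 and Period 2 columns to answer it. If a material share of Period 2 patient-time is below 300 ng/mL, or Period 1 time is above it, the columns no longer separate the two ranges.

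One group deserves particular attention. A patient whose dose is cut for QTcF/JTcF prolongation stays in the Period 2 column at a dose that may not rise again. Patients who proved sensitive to the drug can therefore make the higher-target period look better tolerated than the higher range is.

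**Working it through.** The plan attaches no figure to this point, and its power figures for VO2MAX do not enter. The finding is textual, and two illustrations show its possible size.

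**1. The texts side by side**

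| Item | Protocol | SAP |
|---|---|---|
| Event tables | By dose group, undefined (8.4.2.1) | By period (8.2) |
| Safety comparison | Period 1 versus Period 2 (8.1.2) | Period 1 versus Period 2 (8.2) |
| Rule for assigning events | Not stated | Start date (3.2.1) |
| Daily dose | Tablets recorded daily in a diary (5.4) | Interval estimate, listed only (3.5.1, 6.5) |
| PEX level | Summarized per time point (8.4.4) | Summarized per time point (8.8) |
| Count in target range | None | None |

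The SAP delivers the 8.1.2 comparison. Whether it delivers 8.4.2.1 depends on what dose group means.

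**2. Why period and exposure differ**
- Period 1 has 56 days, and the first 14 are at a fixed 70 mg for everyone (Protocol 4.4.1).
- Doses of 35-210 mg are available in both periods. Only 245 and 280 mg are specific to Period 2 (Protocol 4.4.3).
- Table 4.1 has Period 1 rows for levels above 300 ng/mL, up to above 1200.
- Of ultra-rapid metabolizers, Protocol 2.8 says: "These subjects may not reach the target therapeutic level".
- After a QTcF/JTcF reduction the dose is not increased in either period (Protocol 4.4.4).
- In general only one adjustment is made per two weeks (Protocol 4.4.3), and results arrive 3-5 days after sampling (Protocol 4.4.2).

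**3. Illustration: time below range in Period 2**

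Assume that level is proportional to dose and settles at once. Take a patient at 101 ng/mL on 2 tablets at Week 6, with no change made then. The Period 2 column of Table 4.1 adds one tablet for levels of 101-300.

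Level after each step = 101 × tablets / 2:
- Week 8: 3 tablets, 152 ng/mL
- Week 10: 4 tablets, 202 ng/mL
- Week 12: 5 tablets, 252 ng/mL (252.5 before rounding)
- Week 14: 6 tablets, 303 ng/mL

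The Week 14 visit is Day 99 and Period 2 starts on Day 57. Time below 300 ng/mL is (99 − 57) + 3 to 5 = 45 to 47 of 56 days. Every event in that time is a Period 2 event.

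A patient at 250 ng/mL on 2 tablets would be at 375 after the Week 8 step, so the delay varies widely between patients. Levels that rise faster than dose would shorten it; slow accumulation would lengthen it.

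**4. Illustration: effect on the by-period difference**

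Assume the proportion of patients with an event is 10% in the low range and 30% in the high range, with all Period 1 patients in the low range. Let m be the share who stay below range throughout Period 2.

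Period 2 rate = 0.30(1 − m) + 0.10m, so the difference from Period 1 = 0.20(1 − m).

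| m | Period 2 rate | Difference (points) | Expected patients with event, of 30 (Period 1: 3.0) |
|---|---|---|---|
| 0 | 30% | 20 | 9.0 |
| 0.10 | 28% | 18 | 8.4 |
| 0.25 | 25% | 15 | 7.5 |
| 0.50 | 20% | 10 | 6.0 |

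**The case against.** The strongest reply is that there is no departure from the protocol. In a single-arm study with two sequential targets, dose group can naturally be read as the two periods, and Protocol 8.1.2 specifies that comparison. On this reading SAP 12 has nothing to list. This stands in part: a reader might infer a flat contradiction, but the documents support only an undefined term whose treatment is unexplained.

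Three further inferences go too far:
- *That attained exposure is ignored.* Days on drug are summarized, daily dose is listed, and PEX is summarized by visit with mean, SD, median, minimum and maximum (SAP 5.4, 8.8). Mean PEX level is a covariate in the VO2MAX and 6MWT models (SAP 7.1, 7.2). The gap concerns the adverse event tables and the missing count in range.
- *That the SAP declares out-of-range patients to be in range.* Its columns are labelled as periods. The equation of period with range is one that a reader would make.
- *That a failed titration could not be recognized.* Visit summaries and listings for about 33 patients would show a gross failure. A count would show it directly.

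Serious events already get more. A PEX sample is sought for each one (Protocol 7.7.1), a level above 1,200 ng/mL is itself reportable as serious (Protocol 7.10), and the event record carries an overdose flag (SAP 3.2.1). None of this places ordinary events in an exposure band.

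**Conclusion.** The point holds as a cheap improvement and an ambiguity to settle; it does not make the planned tables wrong. The by-period tables are legitimate. They cannot by themselves answer the low versus high exposure question, and the SAP adds nothing for adverse events that could.

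The size is unknown. The documents give no distribution of Period 1 doses or of levels at a given dose, so no share of patients unable to reach 300 ng/mL can be derived. Table 4.1 also raises the Period 1 dose only at levels of 100 ng/mL or below, so levels cannot be taken as spread evenly over 100-300 at the higher Period 1 doses. The two illustrations show mechanism and scale under stated assumptions and are not predictions.

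The direction, toward no difference, assumes that event risk rises with PEX level. It is probable rather than certain, because the periods are consecutive and risk that changes with time on drug could move the contrast either way.

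**What to change.** 1. **SAP 8.2.** Define dose group. Keep the by-period tables. Add supportive summaries by daily dose at onset and by most recent PEX level before onset: <100, 100-300, >300-500 and >500 ng/mL, plus *no prior level* for events before the first Day 8 result. Use patient-time in each category as denominator. State the source of dose at onset, because the SAP 3.5.1 estimate averages over any change within an interval.
2. **SAP 12.** Record how the tables relate to Protocol 8.4.2.1.
3. **SAP 8.8.** Tabulate n (%) below, within and above the target range at Weeks 8 and 16, overall and by CYP2D6 class.
4. **Reporting.** Describe the all-patient Period 2 versus Period 1 contrast as the effect of the titration strategy, not of attained ranges. The VO2MAX estimate in SAP 7.2.1 is adjusted for PEX level and needs its own description.

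The cost is a few tables from data already collected. Their limits should be stated:
- Cells will be sparse in about 33 patients.
- A level can be about two weeks old and may precede a dose change.
- Dose may be lowered because of an adverse event, so dose and event history are confounded.

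The added event tables are therefore descriptive, without tests. A VO2MAX contrast restricted to patients in range at both tests is not proposed, because that subset is selected after baseline.
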